Sample size and Justification: The traditional rule of thumb for sample size in logistic and Cox regression is ten events per predictor.⁷¹⁻⁷³ However, more recent simulation studies have revealed that serious problems aren't experienced until the number drops below five events per predictor.⁷⁴ Given the close association between logistic, Cox, and proportional odds regression models, these studies should provide a reasonable benchmark for sample size determination for our study. Thus, we adopted a rule of seven events per predictor in determining an appropriate sample size. Assuming that 1 contextual-level factor, 2 clinic-level factors, and seven patient-level factors (one socioeconomic, one cognitive, one psychological, one social, one related to accessibility to clinics, and one related to health status) will be significant at the 0.20 level in bivariate proportional odds models and that we'll need five additional terms due to polynomial trends or predictor-by-time interaction effects, our initial models for backward selection will require 105 events. We anticipate that 20% will be lost to follow-up in the first six weeks and 5% will be lost each year thereafter. Thus, for our loss to follow-up model we only require 378 participants.

However, we expect a cumulative MTCT rate of 5% by 24 months that suggests we will need 2,100 participants for this analysis assuming complete follow-up. Accounting for the expected drop-out, we will need to recruit $2100/(0.8*0.95*0.95) = 2,909$ participants. Assuming an average of 10 HIV diagnoses per year at eligible clinics, we will need to enroll in about 105 MCH clinics (3 per districts) in the first three years of the study.

C. Measurement / Instrumentation

Outcomes and measurement: Key programmatic outcomes that will be considered include: loss-to-follow-up (the proportion of HIV+ pregnant women initiated on ART for whom the whereabouts is unknown), retention in care (proportion of participants who are known to be receiving care), non-adherence to scheduled visits (proportion of participants whose whereabouts is unknown or who are in care but have missed at least one scheduled visit over the evaluation period), virological suppression (undetectable viral load), and MTCT rates (proportion of infants born to participating women who are tested positive for HIV).

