In 2010, as part of our technical support to the implementation of PMTCT in Kinshasa, we developed and supported the implementation of a mother-infant register in 105 MCH clinics to monitor PMTCT care provided in these clinics. The registry was modeled after the WHO's Three Interlinked Patient Monitoring Systems for HIV Care/ART, MCH/PMTCT (including malaria prevention during pregnancy), and TB/HIV: Standardized Minimum Data Set and Illustrative Tools. The register is used to track important HIV care events among HIV-infected pregnant women and subsequently their HIV-exposed infants, from the first contact with the ANC clinic through delivery and the effective linkage of the mother-infant pairs to HIV care and treatment (C&T) services. The following key information is documented in the register: a maternity code that is used to link mother and infant, address and telephone number, gestational age at HIV diagnosis, date of birth, date of reference to HIV C&T if any, date of first visit at C&T and a code number assigned to the mother at C&T, and other information necessary to calculate PEPFAR's PMTCT indicators. For mother-infant pairs who still need to integrate HIV C&T services after delivery, information on infant feeding practices, cotrimoxazole prophylaxis at subsequent visits, date of first sample collection for early infant diagnosis at six weeks and the result, a second sample collection and result at nine months, and eventually a serological test at 18 months for all infants with HIV-negative PCR results is also documented. For real time use of information in the register, nurses who supervised the implementation of PMTCT technical assistance were each equipped with a laptop including the electronic version of the register (in the open-source software Epi-info) and at each clinic visit, they extracted information for the register into the electronic database and returned the updated database to the central team. The same scheme was used for monitoring in our study on conditional cash transfers with a group of nurses who successfully visited on a regular basis the 90 MCH clinics that were enrolled to extract the data in the electronic database. Because of its success, the register has been adapted by the PNLS for the monitoring of Option B+. We will rely on the register to obtain information on the outcomes with study nurses visiting the clinics on regular basis to extract key information for the study into the database.

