Table 1. Outcomes and definitions

Outcomes	Definition
Primary	
loss-to-follow-up	Proportion of HIV+ pregnant women initiated on ART for whom the whereabouts is unknown
Timely infant HIV diagnosis	Proportion of HIV-exposed infant with an appropriate HIV test result
Secondary	
Timely ART initiation	Proportion of HIV-infected participants (mother and infant) initiated on ART within two weeks of diagnosis
Retention in care	Proportion of participants who are known to be receiving HIV care
Non-adherence to scheduled visits	Proportion of participants whose whereabouts is unknown or who are in care but have missed at least one scheduled visit over the evaluation period
Virological suppression	Proportion of participants with undetectable viral load
MTCT rates	Proportion of infants born to participating women who tested positive for HIV
Survival	Proportion of participants known to be alive

For key laboratory tests, CD4 count is generally available free of charge at decentralized locations (over 70 MCH clinics) in Kinshasa and is done at HIV diagnosis and every six months. Viral load measurement is accessible at the national reference laboratory in downtown Kinshasa at a subsidized cost of \$25 or at private facilities (Dream, Doctors Without Borders—MSF) at higher cost per test and is recommended for every patient on ART at least once a year. We have budgeted this to ensure that each participant has at least one viral load measurement at enrollment and every year thereafter during this study.

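### As worded, the secondary outcome non-adherence to scheduled visits omits women known to have stopped HIV care, so they score better than women in care who missed one visit

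*Combined protocol and SAP*

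**What the plan says.** All references are to the combined protocol and SAP.

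- **Non-adherence to scheduled visits (secondary), Table 1 in section III.C:** "Proportion of participants whose whereabouts is unknown or who are in care but have missed at least one scheduled visit over the evaluation period". The opening paragraph of III.C gives the same rule: "non-adherence to scheduled visits (proportion of participants whose whereabouts is unknown or who are in care but have missed at least one scheduled visit".
- **Loss to follow-up (primary), Table 1:** "Proportion of HIV+ pregnant women initiated on ART for whom the whereabouts is unknown".
- **Retention in care (secondary), Table 1:** "Proportion of participants who are known to be receiving HIV care".
- **Outcome source, section III.C:** "We will rely on the register to obtain information on the outcomes with study nurses visiting the clinics on regular basis". The fields listed for the register include "a maternity code that is used to link mother and infant, address and telephone number".
- **Expected attrition, section III.B:** "We anticipate that 20% will be lost to follow-up in the first six weeks and 5% will be lost each year thereafter".
- **Comparison, section III.D, statistical analyses for Aim 2:** outcome frequencies are compared between arms. No rule is given there for women who are located but out of care.

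**The concern.** The numerator has two parts: whereabouts unknown, or in care with a missed visit. Table 1 itself allows a third state. Loss to follow-up turns on whereabouts and retention turns on receipt of care, so a woman can be neither lost nor retained. She may have refused further visits or stopped treatment while still living at a known address. The non-adherence rule does not mention her, and nothing elsewhere excludes her from the denominator or classifies her.

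Two things are at stake. First, the outcome orders women wrongly: attending nothing scores better than missing once. Second, the outcome responds to information as well as to attendance. When a woman who has quit moves from unknown to known, she leaves the numerator although no visit has been kept. If one arm gained more such information than the other, part of any difference in this outcome would reflect knowledge of whereabouts and not visits attended.

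**Working it through.** **Step 1. Classify every state.** The completed rule adds women known to be alive and no longer receiving care. The table covers living women who have not transferred; deaths and transfers are taken up under the fix.

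| Whereabouts | In care | Missed a visit | Rule as written | Completed rule |
|---|---|---|---|---|
| Unknown | No | No | Event | Event |
| Unknown | No | Yes | Event | Event |
| Known | No | No | **Not an event** | Event |
| Known | No | Yes | **Not an event** | Event |
| Known | Yes | No | Not an event | Not an event |
| Known | Yes | Yes | Event | Event |

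The rules differ only in the two states where the woman is located and out of care.

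**Step 2. Reproduce the plan's attrition (section III.B).**

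- Cumulative loss L = 1 - 0.8 x 0.95 x 0.95 = 1 - 0.722 = 0.278.
- Events required: 7 x (1 + 2 + 7 + 5) = 105, as stated.
- Loss-to-follow-up model: 105 / 0.278 = 377.7, rounded up to 378, as stated.
- Transmission model: 2,100 / 0.722 = 2,908.6, rounded up to 2,909, as stated.

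So 27.8% is the loss rate behind the plan's own figures.

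**Step 3. Effect of locating women.** Let t be the share of lost women who are located alive and still out of care, and m the share of women in care with at least one missed visit. The documents give neither, so both are assumptions.

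- Rule as written: L(1 - t) + (1 - L)m
- Completed rule: L + (1 - L)m
- Difference: L x t, whatever the value of m

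| m | t | As written | Completed | Difference |
|---|---|---|---|---|
| 10% | 0 | 35.0% | 35.0% | 0 |
| 10% | 25% | 28.1% | 35.0% | 7.0 points |
| 10% | 50% | 21.1% | 35.0% | 13.9 points |
| 30% | 0 | 49.5% | 49.5% | 0 |
| 30% | 25% | 42.5% | 49.5% | 7.0 points |
| 30% | 50% | 35.6% | 49.5% | 13.9 points |
| 50% | 0 | 63.9% | 63.9% | 0 |
| 50% | 25% | 57.0% | 63.9% | 7.0 points |
| 50% | 50% | 50.0% | 63.9% | 13.9 points |

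**Step 4. Effect on the arm comparison.** If L and m are equal in both arms, the rule as written produces a difference of L x (t in one arm - t in the other). A 10 percentage-point gap in t gives 0.278 x 0.10 = 0.0278, about 2.8 points. If the arms locate women equally, the difference is zero, although the level is understated in both.

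**The case against.** **In care is undefined.** A woman usually quits by missing a visit. If the phrase means in care at some time in the evaluation period, the second part of the rule would catch her. The documents define neither term, so the reading cannot be excluded. The text is in the present tense, however, and nothing supports the wider sense. If that was intended, it has to be written down.

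**The omitted state may seldom be recorded.** The register fields listed in section III.C do not include stopping care or refusal. A woman who stops attending may simply be scored as unknown, and therefore as non-adherent. This stands as a limit on size: the documents do not show how often the state would occur. It does not remove the gap, because Table 1 already requires whereabouts and receipt of care to be judged separately.

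**Retention exposes the problem.** It scores the same woman as not retained, so a reader could see the discrepancy. That does not correct the non-adherence result, which is a separate outcome.

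**Bias toward the intervention.** A reader might infer that the rule favours CQI, because monthly supervision and action plans are described only for intervention clinics. The documents do not support this. They describe no tracing procedure, do not name tracing in the CQI package, and leave the content of action plans to the QI teams. Contact details in the register make locating women possible, but register extraction and interviews are described for participating clinics generally.

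**Conclusion.** The gap in the definition is real and stands in both places where the rule is given. Read literally, a woman known to have stopped care counts in the denominator only, and locating a lost woman improves the outcome with no change in attendance. This is a scoring error in one secondary outcome. No sample-size figure depends on it.

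Bias between the arms is possible but not established, and neither is its direction. The figure of 2.8 points per 10 percentage-point gap is an upper-bound illustration. It assumes 27.8% loss in both arms, the same missed-visit rate in both, and that the women making up the gap are alive, still out of care and not transferred. In practice some located women will have died, transferred or returned, so a given gap in the share located for any reason would produce a smaller shift of this kind.

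**What to change.** In Table 1 and in the opening paragraph of section III.C, define the numerator as women who meet any of these:

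1. whereabouts unknown;
2. known to be alive and no longer receiving HIV care;
3. in care with at least one missed scheduled visit.

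Add that visits count as due only up to death or documented transfer to care elsewhere. Those women also fall outside the present wording, and without this clause they could be misclassified under the new one. State what in care means and over what period it is judged.

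**Cost.** The change is one definition in two places, made before analysis. In-care status and death are already needed for the retention and survival outcomes. Transfer has to be documented: the register lists dates of referral and of first visit at HIV care and treatment services, but the team should confirm that it also captures stopping care and transfer elsewhere, and add a status field if it does not. Measured non-adherence may be somewhat higher than under the literal rule.

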
I. Objectives

The study has two specific objectives:

- 1- **To identify modifiable health delivery system factors associated with retention in care and sustained virological suppression in HIV-infected women in MCH clinics.** We will use surveys of health facilities, including selected staff, and service beneficiaries (HIV infected mothers) to collect data on key characteristics of the service delivery's organization and providers' and patients' perspective of the HIV care delivery performance. Proportional odds models will be used to identify key modifiable characteristics associated with the main outcomes (LTFU, virological suppression, and MTCT rate).
- 2- **Evaluate the effectiveness of CQI interventions in improving long-term retention in care and virological suppression in HIV-infected women in MCH clinics.** We will conduct a cluster-randomized trial with health districts as the randomization unit. MCH clinics in the

intervention group, will undergo quality improvement initiatives using participatory data-driven approaches and on-site monitoring and supervisory support.

II. Background and Rationale

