will start with the randomization. At the beginning of this phase, using the baseline data collected in Phase I, we will bring together teams from the health district Bureau (responsible for supervision), and from sites in the intervention group to identify key bottlenecks in the care delivery system. The group will also develop and agree on an action plan to modify the priority bottlenecks and the key indicators to include in the quarterly data for actions reports. As part of the final evaluation of the 5-year CQI intervention in participating clinics and health zones of Kinshasa, we will conduct semi-structured in-depth questionnaires with members of CQI teams in MCH clinics and at the health zone level. These qualitative data will allow to evaluate the intervention's implementation process measures. Specifically, qualitative interviews will allow to: 1) Investigate contextual factors important for the way intervention was understood, implemented, and adopted by participating personnel and administrators of MCH clinics and health zones; 2) Examine factors that impact the application, quality, and sustainability of the intervention; 3) Understand the attitudes towards the CQI intervention at different levels (individual, facility, and health zones) and possibilities of its future use and scale-up in DRC to reduce mother-to-child HIV transmission.

This two-phased approach will provide us time to thoroughly assess the health delivery characteristics for Aim 1. The study will be implemented in Kinshasa, Democratic Republic of Congo (DRC) and in collaboration with the University of Kinshasa's School of Public Health (KSPH).

B. Sample

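### Read literally, the MTCT definition counts infants of unknown status as uninfected in Aim 2, which biases the arm ratio against CQI if CQI raises testing of infected infants

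*Combined protocol and SAP*

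**What the plan says.** Aim 2 here means the CQI trial comparison, as numbered in Section I and in the analysis text of Section III.D (the Summary lists the two aims in the other order).

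- **Definition.** Table 1 (Section III.C) gives the MTCT rate as "Proportion of infants born to participating women who tested positive for HIV". The paragraph on outcomes and measurement in III.C uses the same numerator and denominator. Neither limits the denominator to infants who were tested or whose status is known.
- **Arm comparison.** The Aim 2 analysis text in III.D compares outcome frequencies by an adjusted Pearson chi-square, with logistic regression for baseline imbalance and GEE for clustering, by intention to treat. It gives no rule for an infant without a test result.
- **Aim 1.** The same section models MTCT as discrete-time survival data, and gives drop-out as a reason.
- **Sample size (III.B).** The 5% cumulative MTCT rate leads to a figure "that suggests we will need 2,100 participants for this analysis assuming complete follow-up". Then: "Accounting for the expected drop-out, we will need to recruit" 2,909.
- **Data source (III.C).** "We will rely on the register to obtain information on the outcomes". The register holds a six-week sample, "a second sample collection and result at nine months, and eventually a serological test at 18 months for all infants with HIV-negative PCR results".
- **Status of the outcome.** MTCT is secondary in Table 1. Objective 2 reads "Evaluate the effectiveness of CQI interventions in improving long-term retention in care and virological suppression in HIV-infected women in MCH clinics" and does not name MTCT. The Summary lists MTCT among the main outcomes at 24 months.

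**The concern.** In this definition a missing result works in an arm's favour: the more infected infants go untested, the lower the arm's MTCT rate. Testing is unlikely to be neutral between arms. The two Table 1 primary outcomes are loss to follow-up and timely infant diagnosis, and the CQI teams work on indicators along the PMTCT cascade. If CQI succeeds on those, it will tend to find more of the infections that exist, and the literal MTCT comparison will charge them to the CQI arm.

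At stake is a true reduction in transmission that is understated or hidden. Section III.A plans interviews that cover "possibilities of its future use and scale-up in DRC to reduce mother-to-child HIV transmission". These are qualitative and are no claim of an MTCT effect, but they show why readers will look at the MTCT result. If the denominator is left open, it could also be chosen after the results are seen.

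**Working it through.** **1. The plan's own figure.** (1 + 2 + 7 + 5) terms x 7 events = 105 events. 105 / 0.05 = 2,100. Retention is 0.8 x 0.95 x 0.95 = 0.722, and 2,100 / 0.722 = 2,908.6, rounded up to 2,909. This reproduces. It treats lost participants as not contributing to the MTCT analysis. If they stayed in the denominator as negative, the expected rate would be 105 / 2,909 = 3.61%, not 5%.

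**2. The bias factor.** With no false positives, the observed rate in an arm is true MTCT x P(tested | infected). Hence

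observed RR = true RR x P(tested | infected, CQI) / P(tested | infected, control).

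**3. Inputs for the size.** True MTCT is 5% in both arms (the plan's rate, no true effect). Let s be the share of infants tested and k the risk in untested infants divided by that in tested infants. Then P(tested | infected) = s / (s + k(1 - s)). The documents give neither s by arm nor k, so both are assumed. For control I take s = 0.722, which is the plan's 24-month maternal retention and not an infant testing share; for CQI, 0.80.

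| k | P(tested given infected), control v CQI | Observed rate, control v CQI | Observed RR | True reduction fully hidden |
|---|---|---|---|---|
| 0.25 | 91.2% v 94.1% | 4.56% v 4.71% | 1.03 | 3.1% |
| 0.5 | 83.9% v 88.9% | 4.19% v 4.44% | 1.06 | 5.7% |
| 1 | 72.2% v 80.0% | 3.61% v 4.00% | 1.11 | 9.8% |
| 2 | 56.5% v 66.7% | 2.82% v 3.33% | 1.18 | 15.3% |

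Example, k = 2: control 0.722 / (0.722 + 2 x 0.278) = 0.565; CQI 0.80 / (0.80 + 2 x 0.20) = 0.667; ratio 1.18. The hidden reduction is 1 - 1/RR.

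**4. If only later testing differs.** Suppose half of infections arise after six weeks, 80% of the earlier ones are found in both arms, and 72.2% v 80% of the later ones are found. Control shows 2.5% x 0.80 + 2.5% x 0.722 = 3.805%, CQI 4.0%: RR 1.05.

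**5. Larger gaps, purely assumed.** At k = 0.25, 0.5, 1 and 2, 60% v 80% tested gives RR 1.10, 1.19, 1.33 and 1.56; 40% v 60% gives 1.18, 1.31, 1.50 and 1.71.

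**6. A simple tested-only comparison, for contrast.** Its RR is (s0 + k(1 - s0)) / (s1 + k(1 - s1)), with 0 for control and 1 for CQI. For 72.2% v 80% this is 0.93, 0.96, 1.00 and 1.07 at k = 0.25, 0.5, 1 and 2. It is unbiased only at k = 1, and favours CQI when untested infants are at lower risk.

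**The case against.** **The definition may be a label and not a coding rule.** No text says outright that an untested infant is negative. The sample size and Aim 1 suggest that this was not intended, and a logistic or GEE analysis would ordinarily drop an infant with a missing outcome. If so, the ratios in steps 3 to 5 do not arise and those in step 6 apply. This stands as a limit on how likely the bias is. It does not remove the point: the definition is given twice with the same denominator, nothing in the Aim 2 text overrides it, and the two readings give different answers.

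**Testing may differ little between arms.** Timely testing is not the same as ever being tested, and a pair lost late may already have results. Interviews run to 24 months in each facility, and the Appendix plans infant blood at 6 weeks and 6, 12, 18 and 24 months, neither limited to one arm. This also stands, and it is why the size is open. But neither text says that it supplies infant HIV results, and lost infants give no sample.

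**The outcome matters less for Aim 2.** MTCT is an Aim 1 primary outcome, and there it has a model that allows for drop-out. This stands and limits the weight of the point.

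**A stronger reading.** A reader might infer that the trial is likely to report a significant harm from CQI. The documents do not support that, because it depends on the assumed gap. With equal arms of 2,909 / 2 = 1,454.5 (assumed) and no true effect, the chance of a significant apparent harm (nominal 2.5%) is as follows.

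| Tested, control v CQI | No clustering, k = 0.5 / 1 / 2 | Assumed design effect 2, k = 0.5 / 1 / 2 |
|---|---|---|
| 72.2% v 80% | 5% / 8% / 12% | 4% / 6% / 8% |
| 60% v 80% | 16% / 31% / 50% | 10% / 18% / 29% |
| 40% v 60% | 27% / 41% / 46% | 16% / 23% / 26% |

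The large values need 20-point gaps that nothing in the plan predicts. The background figure of fewer than 40% of exposed infants tested at 2-3 months (Section II) comes from other settings and an earlier time point.

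**Conclusion.** The point holds in a conditional form. By the literal definition an infant of unknown status counts as uninfected in the Aim 2 comparison, which is at odds with Aim 1 and with the sample size. If CQI raises testing of infected infants, the direction of the bias follows by algebra: against CQI.

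The size is unknown. Under the assumed 72.2% v 80% the null ratio is about 1.03 to 1.18, enough to hide a true reduction of about 3% to 15%. It is larger only under larger assumed gaps. These figures rest on no false positives, a 5% true rate and invented testing shares.

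The main risk is a masked benefit on an outcome that is secondary in Table 1. The Table 1 primary outcomes are unaffected. The point should be fixed because the definition, followed as written, can mislead and the repair is cheap. Confidence is medium, since the investigators may already intend to exclude unknowns.

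**What to change.** 1. In Table 1, the III.C outcome text and the Aim 2 analysis, redefine MTCT for the arm comparison as cumulative MTCT by 24 months, and state that infants of unknown status are not counted as negative.
2. Estimate it with the discrete-time model already planned for Aim 1, adding randomised arm and keeping GEE for district and clinic clustering. Infants are at risk only to their last test.
3. State how three groups are handled: infants never tested, deaths before testing, and infants whose first test is late and positive, so that the interval of infection is unknown.
4. Report the share of unknown status by arm.
5. Add a two-sided sensitivity range for the risk in untested infants, for example m = 0.5 to 2 times that in tested infants. For a simple tested-only estimate the adjusted RR is the tested-only RR x (s1 + m(1 - s1)) / (s0 + m(1 - s0)). With 72.2% v 80%, k = 1 and no true effect, this gives 0.90 / 0.861 = 1.05 at m = 0.5 and 1.20 / 1.278 = 0.94 at m = 2. If risks below half are thought plausible, the range should go lower.

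**Cost.** Wording only; no new data. The main analysis assumes that testing is unrelated to infection given covariates, and would favour CQI if untested infants are at lower risk: a simple tested-only comparison gives RR 0.96 at half the risk with 72.2% v 80%. That is why the range is needed. At k = 1 precision barely changes (SE of log RR 0.187 by the literal definition, 0.186 tested-only, 1,454.5 per arm, no clustering). These bias and precision figures are for the simple tested-only comparison; none were computed for the discrete-time model itself.

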We will use a backward selection methodology to build a proportional odds model for each outcome consisting of contextual, clinic-level, and patient-level predictors. Within clinic-level clustering will be accounted for using Generalized Estimating Equations (GEE). Given the large volume of predictors being considered in this aim, we will only include predictors in our initial models for backward selection if significant at the 0.2 level in a bivariate (single predictor) model. At each step of backward selection, variables insignificant at the 0.1 significance level will be removed from the model.

Statistical analyses – Aim 2: The frequencies of outcomes will be compared between the intervention and control groups using adjusted Pearson's Chi-square.⁷⁷ All analyses will be intent-to-treat, meaning that women will be kept in their randomized group independent of whether they actually received (or did not receive) all their care in the group. The intervention and control groups will be compared for baseline prognostic factors and any imbalances that persist after randomization will be adjusted for using logistic regression. Within district- and clinic-level clustering will be accounted for using GEE.

Human subjects' involvement and characteristics

This study will involve HIV-infected pregnant women and their HIV-exposed infants who receive care in one of the maternal and child health clinics providing HIV care in Kinshasa. Clinical record of those participants (mother-infant register) will be accessed by the study team to extract data for the outcomes. In addition those mother will be interviewed on regular basis on sensitive subject

related to their HIV status, social support including relationship with partner. In addition to the discomfort associate with the discussion of such personal topic, there is a potential risk for confidentiality breach associated with the study.

To minimize those risk, all study staff will be retrained on ethical conduct of human subject research. As part of PEPFAR funded routine services for gender-based violence, resource are available at the level of those MCH clinic to provide psychological support for participant who might need them.

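### The secondary outcome Survival drops participants of unknown vital status from the numerator just as it drops deaths, so a retention gain from CQI would read as a survival gain

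*Combined protocol and SAP*

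**What the plan says.** Three rows of Table 1 (Section III.C) bear on this point:

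- Loss to follow-up, a primary outcome: "Proportion of HIV+ pregnant women initiated on ART for whom the whereabouts is unknown".
- Retention in care, a secondary outcome: "Proportion of participants who are known to be receiving HIV care".
- Survival, the last secondary outcome: "Proportion of participants known to be alive".

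The Survival row does not restrict the denominator to participants whose vital status has been established. It also does not say whether mothers and infants are pooled.

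For Aim 2 (Section III.D), the plan states: "The frequencies of outcomes will be compared between the intervention and control groups", using an adjusted chi-square test, with logistic regression for baseline imbalances and GEE for clustering. It has no censoring rule and no rule for unknown vital status. The discrete-time model that allows for drop-out is specified under Aim 1 only, for loss to follow-up and MTCT.

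On attrition, the sample size paragraph (Section III.B) says: "We anticipate that 20% will be lost to follow-up in the first six weeks and 5% will be lost each year thereafter".

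Outcomes are to be taken from the mother-infant register. The fields listed in Section III.C include contact details, referral and visit dates and infant tests, but no date of death and no vital status. The documents describe no tracing of lost participants.

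**The concern.** A participant who cannot be located will not ordinarily be someone the study knows to be alive. Under the Table 1 definition she is in the denominator but not the numerator, which is how a recorded death is treated. The outcome therefore mixes mortality with contact.

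This mixing is not neutral between the arms. The second objective in Section I is to test whether CQI improves long-term retention and virological suppression, so the intervention is meant to change the proportion whose status is known. If it succeeds, the outcome called Survival moves in favour of CQI whether or not a death was prevented. A reader of the results would see a survival difference and could take it as an effect on mortality.

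**Working it through.** **Inputs from the plan.** 20% lost by six weeks and 5% a year thereafter; seven events per predictor with 1 + 2 + 7 + 5 = 15 terms; MTCT of 5% by 24 months (all Section III.B).

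**Assumptions, not in the documents.** Mortality, the size of any fall in loss, equal arms, and the design effect.

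**Step 1: reproduce the plan's figures.**
- Events: 7 × 15 = 105, as in "our initial models for backward selection will require 105 events".
- Followed to 24 months: 0.8 × 0.95 × 0.95 = 0.722, so lost = 1 − 0.722 = 0.278.
- Loss to follow-up model: 105 / 0.278 = 377.7, rounded up to 378, as in "for our loss to follow-up model we only require 378 participants".
- MTCT model: 105 / 0.05 = 2,100, then 2,100 / 0.722 = 2,908.6, rounded up to the stated 2,909.

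All reproduce, so 27.8% is the plan's own working figure for loss by 24 months. The plan gives no mortality rate, effect size or power for Survival, so there is nothing to reproduce for that outcome.

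**Step 2: what the definition measures.** Let L be the proportion lost and m the mortality among those followed. If no lost participant is separately known to be alive, and all deaths among the followed are recorded, the known-alive proportion is K = (1 − L)(1 − m). The share of those not counted who are losses is L / (1 − K). With L = 0.278:

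| Assumed m | K | Losses as share of those not counted |
|---|---|---|
| 0% | 72.2% | 100% |
| 1% | 71.5% | 97.5% |
| 2% | 70.8% | 95.1% |
| 5% | 68.6% | 88.5% |

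**Step 3: effect of retention alone.** With the same m in both arms, the difference in K is (fall in L) × (1 − m).
- 5-point fall, m = 2%: 0.05 × 0.98 = 4.9 points (70.8% to 75.7%).
- 10-point fall, m = 2%: 0.10 × 0.98 = 9.8 points.
- Over m = 0% to 5%: 4.75 to 5.0 points for the 5-point fall, and 9.5 to 10.0 points for the 10-point fall.

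**Step 4: the converse.** With a 5-point fall in loss and 2% mortality among followed controls, K is equal in the two arms when 0.772 × (1 − m₁) = 0.70756. This gives m₁ = 8.3%. The outcome would show no difference although mortality among the followed was 8.3% against 2%.

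**Step 5: chance of a nominally significant result with equal mortality.** With 2,909 / 2 women per arm divided by an assumed design effect, m = 2% and two-sided p < 0.05:

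| Fall in loss | Design effect 1 | 2 | 3 | 5 |
|---|---|---|---|---|
| 5 points | 85% | 56% | 41% | 27% |
| 10 points | 100% | 99% | 95% | 79% |

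At 2,909 / 35 = 83.1 women per district, 1 + 82.1 × ICC gives design effects of 1.8, 2.6 and 5.1 for assumed ICCs of 0.01, 0.02 and 0.05.

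**Step 6: death among those of known status.** In the same scenarios this gives 98% against 98%, an expected difference of zero, provided loss is unrelated to death.

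**The case against.** The strongest defence is that the row states what it measures. It says that status must be known, its wording matches the retention row, and Section III.C introduces the outcomes as programmatic. Survival is also the last secondary row. It is absent from the main outcomes in the Summary and from the narrative list of outcomes, and neither objective mentions mortality. This limits the importance of the point. It does not remove it: the row is named Survival, and the only analysis described for Aim 2 compares frequencies without separating the unknown from the dead.

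Four stronger readings are tempting, and the documents do not support them:

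- **That Survival simply duplicates loss to follow-up.** It nearly mirrors it. Recorded deaths lower Survival without raising loss, a woman out of care but known to be alive still counts as alive, and the loss row covers women while the Survival row may include infants.
- **That 72.2% is a hard ceiling.** It comes from a planning assumption about drop-out, and any lost participant separately known to be alive would raise it.
- **That the trial will report a false mortality conclusion, or that any gain would be retention only.** This is a risk, not a certainty. Better retention could prevent deaths; the defect is that this outcome cannot show which has happened.
- **That a time-to-death analysis can simply use dates already in the register.** No such date is among the listed fields. The list ends with an open-ended category, so capture is possible but not shown.

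**Conclusion.** The point holds as a fault in the stated definition, not merely as missing detail. Applied as written, Table 1 treats unknown status like death, and nothing elsewhere in the document corrects this for Aim 2.

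Under the plan's own 27.8% loss, the measure would mostly reflect contact, and a fall in loss would pass into 'survival' almost point for point with mortality unchanged. The 27.8% follows from the plan. The 1% to 5% mortality, the 5- and 10-point falls in loss, the equal arms and the design effects are illustrations. The calculations also assume that no lost participant is otherwise known to be alive and, for the zero true effect, that loss is unrelated to death.

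The outcome is secondary, so this does not affect the primary comparisons. It should be corrected before any survival result is reported.

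**What to change.** 1. Rename the current measure 'alive and in contact' in Table 1, and state that it will not be interpreted as mortality.
2. Report known alive, known dead and unknown at 24 months postpartum by arm, for mothers and infants separately, with district clustering accounted for.
3. Base any survival comparison on death from any cause as the event, timed from enrolment for mothers and from birth for infants, censored at the date last known alive.
4. Add bounds in which mortality among the lost is a stated multiple of that among the retained, for example 1, 2 and 5.

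**Cost.** Items 1 and 2 need changes to Table 1 and the Aim 2 text and one extra table. Items 3 and 4 are a small added analysis only if dates of death and of last contact are recorded. The sponsor must confirm this; if they are not recorded, a data item and some means of ascertaining deaths would have to be added.

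**Downside.** Censoring assumes that the lost resemble the retained. If deaths are seen mainly among women still in contact, better contact under CQI could bring more deaths to light in that arm and bias the censored analysis against CQI. The three-category report and the bounds should therefore always accompany it.
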